Pain, Enjoyment of Life, and General Activity (PEG) and Patient Global Impressions Scale (PGIC) will be assessed at 6 weeks (midpoint of intervention period one), 12 weeks (Visit 1), 18 weeks (midpoint of intervention period two), 24 weeks (Visit 2), and 36 weeks post-baseline (12 weeks after intervention period two). Basic safety assessments will also be performed at these time points to assess participant tolerability to their current study intervention(s). Patients who are unable to tolerate their assigned study treatment will be educated on how to safely discontinue their current treatment plan but will otherwise remain in the study.

Objectives:

The primary objective is to estimate an algorithm to assign sequences of two cLBP treatments based on phenotypic markers and an individual patient's response to the initial treatment (*i.e.*, a dynamic treatment regime (DTR)) that optimizes effectiveness. as characterized by the primary and secondary endpoints.

The study has the following three secondary objectives:

- Estimate DTRs that optimally balance multiple outcomes, taking into account participant preferences for outcomes including pain intensity, pain interference, physical function, opioid use, depression, anxiety, sleep duration and sleep disturbance.
- Estimate DTRs that incorporate additional phenotypic markers (i.e., deep phenotyping) collected on a subset of participants.
- Assess whether effectiveness is sustained on outcomes collected
 24 weeks after randomization to the second treatment.

Analyses for secondary objectives will utilize the set of primary and secondary endpoints.

The study has the following exploratory objectives:

- Evaluate the comparative effectiveness of individual treatments.
- Evaluate the comparative effectiveness of different treatment regimes (i.e., a particular regime with a given set of rules at each decision point).
- Evaluate the impact of treatment order on outcomes.

Analyses for exploratory objectives will utilize the set of primary and secondary endpoints.

The primary endpoint for the study is 24-week change from baseline in patient-reported pain intensity and interference, measured with the Pain, Enjoyment of Life, and General Activity (PEG) scale.

Secondary endpoints are:

- 24-week change from baseline in pain interference, measured with the 4-item PROMIS Pain Interference scale (PROMIS-PI, 4a)
- Incidence of any opioid use at 24 weeks post baseline.

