- **24-week change from baseline in pain interference**, measured with the 4-item PROMIS Pain Interference scale (PROMIS-PI, 4a) at Visits 0 (baseline) and 2 (24 weeks of treatment)
- Incidence of opioid use, measured by self-report at Visit 2 (24 weeks of treatment)
- **24-week change from baseline in physical function**, measured with the PROMIS-PF Short Form 6b at Visits 0 (baseline) and 2 (24 weeks of treatment)
- 24-week change from baseline in depression score, measured with the PROMIS 4-item depression scale from the PROMIS 29 profile at Visits 0 (baseline) and 2 (24 weeks of treatment)
- **24-week change from baseline in anxiety score**, measured with the PROMIS Emotional Distress-Anxiety scale (PROMIS-EDA 4a) at Visits 0 (baseline) and 2 (24 weeks of treatment)
- **24-week change from baseline in sleep disturbance,** measured with the PROMIS short form 6a at Visits 0 (baseline) and 2 (24 weeks of treatment)
- **24-week change from baseline in sleep duration,** measured at Visits 0 (baseline) and 2 (24 weeks of treatment)

The PEG is a 3-item assessment of pain intensity and interference with enjoyment of life and general activity over the past week. This scale is validated, has low participant burden, is responsive to change, and captures multiple core outcome domains recommended by the Initiative on Methods, Measurement, and Pain Assessment in Clinical Trials (IMMPACT) and that are valued by people who experience chronic pain. ²⁹⁻³¹ In addition, pain intensity was considered the primary outcome of interest by the BACPAC Patient Advisory Board. Pain interference with be assessed using PROMIS-PI, which has demonstrated reliability and validity across diverse populations for the assessment of the degree to which pain interferes with physical, mental, and social activities. ³²⁻³⁴ Self-reported opioid use is included as a secondary endpoint. Additional secondary endpoints of physical function, depression, anxiety, and sleep disturbance are patient-centered and will be assessed using validated instruments from the PROMIS measure set. Depression and anxiety, common among individuals who experience chronic pain, negatively affect quality of life. ³⁵ Finally, PGIC is of key importance in the determination of response to treatment following the first randomization because it is valued by patients, integrates both positive and negative factors about treatment, and is responsive to change under pharmacologic and

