10.4.4. MEASURES TO MINIMIZE BIAS: RANDOMIZATION AND BLINDING

The **first-stage randomization** will use a randomized version⁶¹ of the Minimization method^{62,63} to maintain marginal covariate balance. Minimization is an alternative to stratified permuted block randomization for maintaining (marginal) covariate balance across treatments that is better equipped to handle a larger number of factors to balance on. When a participant is randomized, a measure of the marginal discrepancy between treatments is calculated and the patient is randomized using a biased coin method where whichever treatment would make the discrepancy smallest has a higher probability and the other treatments have equal, smaller probabilities. Covariates included in minimization algorithm:

[figure not shown]
- Willingness to participate in deep phenotyping (yes/no)
- Depressive or anxiety symptoms (yes/no)
- Duration of pain symptoms (<5 years/≥5 years)
- Current use of opioid treatment (yes/no)

A total of approximately 740 participants will be randomized to ACT (n=185), duloxetine (n=185), ESC (n=185), and EBEM (n=185) and which will require recruitment of approximately 820 participants, anticipating that 10% will not be randomized due to failure to meet eligibility criteria at the end of the run-in phase and an estimated 15% will be lost to follow-up over the course of the study. Participants who did not complete required run-in procedures will not be randomized. In order to assign equal numbers of participants to each of the 4 study interventions, randomization probabilities will account

for the fact that certain participants, e.g., because of a contraindication, may be eligible for only 3 of the 4 treatments.

Second-stage randomization will occur at the end of the first treatment period. Response to treatment will be assessed using the PEG and PGIC. Based on these scores, individuals will be grouped into 4 response classes.

- Group 1 participants (PGIC 1-2 and PEG <4) are assigned to maintain the first-line treatment.
- Group 2 participants (PGIC 1-2, PEG ≥4) are assigned to maintain the current treatment and augment with a randomly selected additional treatment.
- Group 3 participants (PGIC 3-4) are randomized to an **augmentation treatment or to switch** to a new treatment.
- Group 4 participants (PGIC 5-7) are randomly assigned to switch to a second-line treatment.

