12. STUDY ASSESSMENTS AND PROCEDURES

12.1. EFFICACY ASSESSMENTS

Study outcomes will be assessed by self-report using a series of validated instruments to measure pain intensity and interference, physical function, depression, anxiety, sleep disturbance and duration, and opioid use. Patient-reported outcome measures will be administered at study baseline as well as at 12-and 24-weeks following first-stage randomization using a web-based survey platform. The primary endpoint is based on the Pain, Enjoyment of Life, and General Activity (PEG) scale, a 3-item assessment of pain intensity and interference with enjoyment of life and general activity over the past week. Response values for each item range from 0 to 10 and the average score across the three items will be used as the outcome value.

Secondary outcome assessments include:

- PROMIS Pain interference scale (PROMIS-PI, 4a)
- Current use of opioid medication on a daily basis
- PROMIS Physical Function (PROMIS-PF Short Form 6b)
- PROMIS 4-item Depression scale (from the PROMIS 29 profile)
- PROMIS Emotional Distress-Anxiety scale (PROMIS-EDA 4a)

- PROMIS Sleep disturbance (PROMIS short form 6a)
- Sleep duration (reported number of minutes asleep per night over the past month)

Primary and secondary endpoints

- Primary endpoint: 24-week change from baseline in patient-reported pain intensity and interference, measured with the Pain, Enjoyment of Life, and General Activity (PEG) scale at Visits 0 (baseline) and 2 (24 weeks of treatment)
- **24-week change from baseline in pain interference**, measured with the 4-item PROMIS Pain Interference scale (PROMIS-PI, 4a) at Visits 0 (baseline) and 2 (24 weeks of treatment)
- Incidence of opioid use, measured by self-report at Visit 2 (24 weeks of treatment)
- **24-week change from baseline in physical function**, measured with the PROMIS-PF Short Form 6b at Visits 0 (baseline) and 2 (24 weeks of treatment)
- **24-week change from baseline in depression score**, measured with the PROMIS 4-item depression scale from the PROMIS 29 profile at Visits 0 (baseline) and 2 (24 weeks of treatment)
- **24-week change from baseline in anxiety score**, measured with the PROMIS Emotional Distress-Anxiety scale (PROMIS-EDA 4a) at Visits 0 (baseline) and 2 (24 weeks of treatment)
- **24-week change from baseline in sleep disturbance,** measured with the PROMIS short form 6a at Visits 0 (baseline) and 2 (24 weeks of treatment)

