#### **Analysis Populations**

The population used for statistical analysis consists of the 805 randomized participants to a Stage 1 treatment.

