## **Analysis**

#### **Analysis Methods**

A linear mixed-effect model (LMM) was used to model the least squares mean of the primary and secondary outcomes at Visit 2 (Week 24) by the Stage 1 treatment assignment for all continuous outcomes. Random intercepts and a linear random slope for time were included to account for subject-level variability. The randomization and minimization algorithm variables are included as

fixed effects. Week indicators as fixed effects were included to model non-linear effects of time. An additional fixed effect was included for the number of treatments a participant was eligible for at the baseline visit. Estimation was conducted using REML and modern optimization approaches with the lme4 package in R. Least squares means were estimated for each Week 24 outcome, along with associated 95% confidence intervals, using the emmeans package in R. Due to the small number of participants on opioids in the BEST Trial sample, we only report counts of participants self-reporting opioid use at Week 24.

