Opioid Incidence	Secondary	Opioid incidence reported at Visit 2 (Week 24)	Self-reported Yes/No/Not Sure response to a single question, "Are you currently taking any opioid pain medication on a daily basis?"	Counts

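### The secondary endpoint labelled incidence of any opioid use is in fact a Week 24 count of self-reported current daily use, with no denominator and no link to baseline use

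*Protocol*

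**What the plan says.** The documents describe this endpoint in four ways.

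- **Protocol 4.1 (Synopsis, Endpoints):** "Incidence of any opioid use at 24 weeks post baseline".
- **Protocol 6, repeated in 12.1:** incidence of opioid use by self-report at Visit 2. The word *any* is gone, and daily use is not mentioned in the label.
- **Protocol 12.1, list of secondary assessments:** "Current use of opioid medication on a daily basis".
- **SAP, Outcome Definitions:** the outcome is named opioid incidence and defined as a "Self-reported Yes/No/Not Sure response to a single question", which reads "Are you currently taking any opioid pain medication on a daily basis". The analysis method is counts.

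Under Analysis Methods the SAP cites the small number of participants on opioids and says "we only report counts of participants self-reporting opioid use at Week 24". Under Analysis Populations it says "The population used for statistical analysis consists of the 805 randomized participants to a Stage 1 treatment".

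Baseline opioid use is not among the exclusions in protocol 8.2. It is a minimisation factor in protocol 10.4.4, worded "Current use of opioid treatment (yes/no". The SAP also lists current daily opioid medication as a baseline characteristic, and its Appendix 2 table shell gives this by arm as Yes, No or Not sure.

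**The concern.** The label makes two claims that the measurement does not support. *Any use* suggests that occasional or as-needed use is included, but the item is limited to daily use. *Incidence*, in its usual sense, means new cases among people who were not cases at the start, but nothing restricts the count to baseline non-users.

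Protocol 5.1 says the precision medicine approach may help reduce reliance on opioids, and 5.2.2 names lower long-term opioid use as a possible benefit. What bears on that aim is who started and who stopped. The other six secondary endpoints in protocol 4.1 are changes from baseline. This one takes no account of baseline, so a participant who continues is counted like one who starts, and a participant who stops does not appear.

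A bare count also has no stated denominator. Participants with no Week 24 answer simply do not appear in it, and the SAP gives no rule for Not Sure.

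**Working it through.** The documents give no rate, effect size or power for this endpoint, and the sample size in protocol 13.2 rests on PEG. There is no planned figure to reproduce, so the check compares label with measurement and then illustrates the scale on assumed values.

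**Step 1: frequency.** In the SAP item, *any* qualifies the type of opioid, while the closing phrase limits frequency to daily. A participant with only non-daily use should answer No. The item therefore measures daily use.

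**Step 2: timing and baseline status.** The item asks about current use, so it records a state at Week 24. Three facts put baseline users in the count: protocol 8.2 does not exclude them, protocol 10.4.4 balances on opioid use, and the SAP analyses all those randomised. That they are counted is an inference, but no text removes them. The quantity is a point prevalence.

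**Step 3: denominator.** SAP Appendix 3 gives 805 randomised to Stage 1 and 683 to Stage 2. The difference is 805 − 683 = 122, and 122/805 = 15%. The number answering at Week 24 is not given, so the count cannot be turned into a proportion.

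**Step 4: count with no new users (assumed rates).** Suppose a share b used daily at baseline, all of them continued, and nobody started. The count is then N × b.

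| b (assumed) | N = 683 | N = 805 |
|---|---|---|
| 3% | 20.5 | 24.2 |
| 5% | 34.2 | 40.3 |

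The N = 805 column is a ceiling, because it needs every randomised participant to answer at Week 24. N = 683 is only a rough stand-in for those followed.

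**Step 5: mixture of continuing and new users (assumed rates, complete data, N = 805).** With persistence p among baseline users and onset i among non-users:

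count = N·b·p + N·(1 − b)·i

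The values tried were b = 2%, 5%, 10%; p = 70%, 90%; i = 0.5%, 2%.

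| Case | b, p, i | Continuing | New | Count | New as share |
|---|---|---|---|---|---|
| Smallest count | 2%, 70%, 0.5% | 11.3 | 3.9 | 15.2 | 26% |
| Largest count | 10%, 90%, 2% | 72.5 | 14.5 | 86.9 | 17% |
| Largest share new | 2%, 70%, 2% | 11.3 | 15.8 | 27.0 | 58% |
| Smallest share new | 10%, 90%, 0.5% | 72.5 | 3.6 | 76.1 | 5% |

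Over the whole grid the count runs from about 15 to 87, new users from about 4 to 16, and new users as a share of the count from 5% to 58%. The SAP's remark that few participants were on opioids makes the upper end of b less plausible, but it gives no number. The count alone does not identify the number of new users.

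**The case against.** The strongest reply is that *incidence at 24 weeks* may loosely mean occurrence at 24 weeks. The label is tied to Visit 2, no text speaks of new use or onset, and the SAP prints the item in full. A careful reader would see that current daily use is counted. This stands as far as it goes and softens the incidence half. It does nothing for the conflict between any use and daily use.

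Three stronger readings are tempting, and the documents do not support them.

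- **That the count will be taken as new use and mislead on opioid reliance.** This is conjecture. The SAP nowhere claims to count new use, plans no hypothesis test, and tabulates baseline daily use by arm, so baseline and Week 24 totals can be set side by side. Those totals still cannot separate starting, continuing and stopping.
- **That the trial misses non-daily use altogether.** Only this endpoint's item does so. Protocol 14.1.12 provides for concomitant medications to be entered and coded, 9.1 says questionnaires cover medication use, and a current opioid use questionnaire is scheduled at baseline and Weeks 12, 24 and 36 (Section 16, Appendix A). Its full content is not shown.
- **That 24–40 spurious cases is an estimate.** The 3–5% share is assumed, and the figure needs complete follow-up and full persistence.

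It is also fair that splitting small numbers by arm and by transition gives sparse cells. That limits what can be concluded from the table but is no reason to leave it out.

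**Conclusion.** The point holds as a mismatch between label and measure, together with an incomplete presentation. As planned, the endpoint is a point prevalence of self-reported current daily opioid use at Week 24, reported without a denominator, a baseline split or a rule for Not Sure. The any-versus-daily conflict is plain from the text. The inclusion of baseline users is inferred from eligibility, from the analysis population and from the absence of any exclusion rule.

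The size of the distortion cannot be determined from the documents. The ranges above show only that continuing users could be anything from somewhat under half of the count to nearly all of it.

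Severity is minor to moderate. This is a descriptive secondary endpoint with no test and no bearing on the sample size, and the correction uses data already collected.

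**What to change.** 1. **Relabel** the endpoint in the protocol and the SAP as *self-reported current daily opioid use at Week 24 (prevalence)*. Any-use incidence cannot be recovered from this item, so the label has to follow the measure.
2. **Report by Stage 1 arm** the number answering the item at Week 24, with Yes, No and Not Sure shown separately.
3. **Cross-tabulate** Week 24 against the baseline daily-use item, showing new daily use among baseline non-users and continued or stopped use among baseline users. Take baseline status from the daily-use item in the SAP's baseline table, not from the minimisation factor. The factor's wording is not limited to daily use and has no Not Sure category, so if it includes as-needed users, crossing it with the Week 24 item would show continuing as-needed users as having stopped.
4. **Keep the table descriptive** and say that cells may be sparse.

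The cost is a wording change and one small table. No new data, model or participant contact is needed.

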4.2. SCHEMA

4.3. SCHEDULE OF ACTIVITIES (SOA)

See Appendix A

5. INTRODUCTION

5.1. STUDY BACKGROUND AND RATIONALE

Chronic low-back pain is a highly prevalent pain condition among adults that diminishes both physical and psychosocial wellbeing⁴. Chronic low-back pain lasting three months or more with pain occurring on most days affects 10-20% of adults¹, and 28% report back pain in the past three months⁴. Chronic lowback pain contributes to lost employment, disability, and, by some estimates, \$100 billion in health care expenditures. In the 2010 Global Burden of Disease Survey, low-back pain was ranked highest among 291 conditions in terms of years lived with disability². Sufferers, who are disproportionately women and people with low socioeconomic status, contend with physical pain, limited mobility, and mental health symptoms². Chronic low-back pain is second only to cancer in number of opioids prescribed, and opioids are the most commonly prescribed class of drugs for low-back pain, despite limited evidence of efficacy in chronic pain, and the significant risks of side effects, addiction, and death¹⁶. While a broad range of treatments exists, current treatments do not adequately resolve chronic low-back pain for most patients. Systematic reviews of common treatments find small to moderate evidence for efficacy for some treatments¹⁷⁻¹⁹. In clinical practice, first-line recommendations for chronic low-back pain are often non-steroidal anti-inflammatory drugs (NSAIDS) and exercise for patients who experience nonimmobilizing pain, and opioids may still be commonly recommended when other treatments have failed^{20,21}.

Research into optimum treatment for chronic low-back pain is challenged by the diverse etiology of back pain, the varied phenotypes of back pain patients, and difficulty assessing both the cause of pain and treatment effect. Trial design and retention issues limit our understanding of treatments and their effect. While individual trials of single or multi-modal interventions have demonstrated moderate treatment effects, heterogeneity of trial design, outcomes, and populations stymie large-scale systematic reviews²² as well as reviews of specific treatment approaches¹⁹. These methodological factors highlight the need for large-scale trials with standardized measures, treatments, and outcome measures. Additional research priorities include patient phenotyping and sub-group stratification and the development of pharmacological and non-pharmacological first-line treatments for chronic low-back pain²³. The proposed BEST trial will harmonize recruitment, enrollment, data collection, and retention strategies across multiple sites, each of which will recruit from a diverse population of chronic low-back pain patients. Drawing on expertise from within and outside of the consortium, sites will adopt ambitious recruitment and retention goals. Given historic underrepresentation of minority communities in research, the consortium will closely monitor recruitment of underrepresented communities and initiate oversampling, as needed.

The NIH supports the discovery and testing of novel non-addictive pain treatments to stem the ongoing opioid crisis and to support the translation of scientific finding into clinical practice². BACPAC, a funded component of the NIH's Helping End Addiction Long-term (HEAL) initiative, is a multisite consortium which will advance treatment of chronic low-back pain by applying a precision medicine approach to identify specific treatments or combinations of treatments that are most effective in identifiable subgroups of participants.

In line with these objectives, the BACPAC consortium will conduct a multisite clinical trial, which will incorporate four interventions whose components have been studied previously and have been clinically proven to be effective for some populations. The interventions to be included in the trial are: enhanced self-care (ESC), which incorporates self-management techniques and education, acceptance and commitment therapy (ACT), duloxetine, and evidence-based exercise and manual therapy (EBEM)^{10,13-15}. The trial will build on this knowledge base by applying a precision medicine approach to these proven interventions to determine the optimal treatment for specific participant subgroups. This precision medicine approach is designed to estimate an algorithm to assign sequences of two cLBP treatments based on an individual participant's changing response and phenotypic markers and may help to reduce reliance on opioids for many cLBP patients.

